3.2. Sampling and randomization

Study site: The National Center for Maternal and Child Health (NCMCH) is purposely selected as a study site. Approximately 50% of all deliveries in Ulaanbaatar occur in the center and there are about 11,000 live births annually. As the center is a specialized tertiary care level teaching hospital, it is responsible for providing services for follow-up ultrasound controls and treatment of DDH cases in Ulaanbaatar. There are two term-delivery units with 6 neonatologists/screeners, a preterm-

delivery unit with 6 neonatologists/screeners and a pediatric radiology unit with 6 radiologists. Data will be collected from September 2019 to March 2021.

Sample size calculations: The primary outcome of interest is dichotomous (Graf Type 1 or non-Type 1 hips). If we assume that 10% of the subjects on the non-swaddled group has a non-Type 1 hip and it is of clinical relevance only if we observe a 30% (effect size) absolute non-improvement for those on the swaddled group (i.e. 40% of the subjects will have a non-type 1 or worst hip).

For a two-sided test of 5%, a formula to calculate the sample size is given by

$$N (\text{size per group}) = c * \frac{\pi_1(1 - \pi_1) + \pi_2(1 - \pi_2)}{(\pi_1 - \pi_2)^2}$$

where $c = 7.9$ for 80% power, and $\pi_1=0.2$ and $\pi_2=0.4$

For a 80% power, we have $N (\text{size per group}) = 7.9 * [0.1 (1 - 0.1) + 0.4 (1 - 0.4)]/(0.1-0.4)^2 = 29$

Hence minimum $29 * 2 = 58$ subjects are needed.

In order to increase the statistical power, and assuming at least a 20% dropout, it is decided to include about 40 subjects in each group.

Sampling: There are 6 neonatologists/screeners at post-delivery wards of the hospital who perform the hip ultrasound screening. Out of the 6 neonatologists/screeners, one neonatologist will be assigned as a data collector for the study to reduce a baseline diagnostic bias. On the first days after birth, all newborns of the data collector will be screened using Graf's method of ultrasound according to the Mongolian National Guideline.⁸ After the screening, we will generate a list of all newborns with Graf Type 2a hips on daily basis. All term newborns with Graf Type 2a cases (physiologically immature) will be eligible for the study.

Subject inclusion criteria

Predefined inclusion criteria will be:

1. Term newborns with confirmed Type 2a hips
2. Parents who are able to return for the scheduled follow-up ultrasound examination during the study period

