3. Willing to give informed consent
4. Newborns without any symptoms and complaint

Predefined exclusion criteria will be:

1. Newborns with obvious congenital abnormalities (with clear medical consequences)
2. Newborns with needs for intensive care treatment
3. Newborns with low (2499g or less)
4. Newborns with confirmed non-type 2a hips

Randomization sequence will be created using Excel 2007 (Microsoft, Redmond, WA, USA) with a 1:1 allocation using random block sizes of 4 by an independent researcher with no clinical involvement in the trial. After obtaining the consent from the parents, details of the allocated group will be given on colored cards contained in sequentially numbered and sealed envelopes. These will be prepared by the principal investigator and kept in an agreed location on the post-delivery ward. Randomization will take place before discharge when the data collector/neonatologist gives detailed consultation on usual postnatal care of newborns. Corresponding envelopes will be opened

only after the enrolled newborns completed all baseline assessments and it is time to allocate the intervention. Whereas parents allocated to the swaddling group and the research assistants will be aware of the allocated arm, the outcome assessor/radiologist will be kept blinded to the allocation.

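### Allocation concealment is weaker than it need be: the principal investigator prepares ward-held envelopes, and Sections 3.2 and 3.3 disagree on whether written consent and baseline data precede randomisation

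*Protocol*

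**What the plan says.** Protocol Section 3.2 has the sequence created "by an independent researcher with no clinical involvement in the trial". It then describes the carrier: "details of the allocated group will be given on colored cards contained in sequentially numbered and sealed envelopes". On preparation and storage it says: "These will be prepared by the principal investigator and kept in an agreed location on the post-delivery ward". Envelopes are to be opened "only after the enrolled newborns completed all baseline assessments and it is time to allocate the intervention".

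On who is present: "Randomization will take place before discharge when the data collector/neonatologist gives detailed consultation on usual postnatal care of newborns". The same section says that "one neonatologist will be assigned as a data collector for the study to reduce a baseline diagnostic bias", so the person giving that consultation also types the hips at baseline. It adds that research assistants will know the allocated arm, while the outcome assessor (a radiologist) is kept blinded.

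Section 3.3 has research assistants check the inclusion criteria and obtain oral consent. It then describes a second explanation, written consent, the ID number and a baseline questionnaire, and introduces these steps as following randomisation. For families who cannot or will not attend follow-up, Section 3.3 has the principal investigator do the ultrasound at home.

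**The concern.** Concealment depends on nobody who can influence enrolment being able to learn the next arm, and on the family being committed and described before the arm is known. The plan starts well with an independent list-maker. It then passes the list to the principal investigator and stores the result where recruitment takes place.

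Staff and parents know the arms, and Section 6 states the expected result, that swaddling harms Type 2a hips. Several enrolment steps involve judgement: whether parents can return for visits, whether they are willing to consent, and how the study is explained to them. If the arm were known or guessed before those steps were complete, infants could be deferred or families discouraged differently by arm. If written consent is sought after the arm is known, families can also leave differently by arm. Either route can unbalance the groups on factors that bear on the primary outcome, and an intention-to-treat analysis of those who remain does not undo it.

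**Working it through.** No figure in the protocol is at issue here, so the check is mainly a comparison of statements. An illustration of size follows.

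**1. Path of the list.** The independent researcher creates the sequence, the principal investigator prepares the envelopes, and the envelopes are "kept in an agreed location on the post-delivery ward". To fill numbered envelopes with the right cards, the preparer must have the sequence. The independence obtained at generation is therefore lost at the next step.

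**2. Physical safeguards.**
- Stated: sealed, sequentially numbered, and opened only after enrolment and baseline assessment.
- Not stated: opaque, held by someone outside the ward team, or logged when opened.
- The arm is carried by card colour and the next number is always known, so the missing items are the ones that matter.

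**3. Blinding of the assessor.** Section 3.2 says the outcome assessor is blinded. Section 3.3 makes the principal investigator the assessor for families seen at home. Since the principal investigator can know the sequence, the two statements do not fit for those infants. The protocol does not say how many there will be.

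**4. Order of events.**

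| Step | Section 3.2 | Section 3.3 |
|---|---|---|
| Consent | before the allocated group is disclosed | oral before, written after randomisation |
| Baseline data | all complete before the envelope is opened | questionnaire after randomisation and written consent |
| ID number | not mentioned | given only after written consent |

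Reading the consent in Section 3.2 as oral consent would reconcile the first row. It would not reconcile the second: the questionnaire collects birth weight, fetal position, parity and family history, and Section 3.5 counts birth weight, breech delivery, parity and family history among its baseline variables. Section 3.3 already refers to parents by group when written consent is sought, so a family could decline knowing its arm and before it has an ID number.

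**5. Illustration of size.** From the protocol: about 40 per group, so 2 × 40 = 80 allocations; with 20% dropout, 40 × 0.80 = 32 evaluable per arm. Assumed, not in the protocol: no true effect; a 25% non-Type 1 rate; steered infants have 50% risk in the swaddling arm and 5% in the other.

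- No steering: 0.25 vs 0.25.
- 4 of 40 steered per arm: (36 × 0.25 + 4 × 0.50)/40 = 0.275 vs (36 × 0.25 + 4 × 0.05)/40 = 0.230.
- 8 of 40 steered per arm: (32 × 0.25 + 8 × 0.50)/40 = 0.300 vs (32 × 0.25 + 8 × 0.05)/40 = 0.210, a spurious difference of 9 percentage points.

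Summing exact binomial probabilities over all tables that the uncorrected chi-square test rejects at the two-sided 5% level, with 32 per arm, gives rejection rates of 0.052, 0.072 and 0.133. These show how few infants would matter in a trial of this size. They do not estimate what will happen.

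**The case against.** A reader might infer that the next arm can simply be read before an infant is typed and approached, so that all 80 assignments are exposed. The protocol does not support that. The envelopes are sealed and there is an explicit rule on when they are opened. Reading ahead would need a see-through or tampered envelope, and the protocol neither states nor excludes one. Silence on opacity is not evidence of translucent paper, and such detail is often kept in a separate randomisation procedure.

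Other safeguards also count. On-site experts check every examination (Section 3.3), which limits deliberate re-typing of a hip. All Type 2a newborns are listed daily (Section 3.2) and refusals are registered (Section 3.3), so selective approach would leave some trace. Baseline alpha angle is a balance variable, and variables that differ at enrolment enter the adjusted model (Section 3.5). Sealed, numbered envelopes are an ordinary method at a single site.

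All of this stands, and it rules out the stronger reading. It also weakens the illustration, which takes an unadjusted test and invented risks. It does not answer four points: the list passes to the principal investigator, that person is also an assessor, the two sections give different orders for consent and baseline data, and image review and covariate adjustment do not reach deferral or discouragement on unmeasured grounds such as a family's attitude.

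**Conclusion.** The concern holds in a limited form. What the protocol itself fixes (preparation by the principal investigator, storage on the ward, randomisation at the consultation of the neonatologist who types the hips) makes concealment weaker than it need be. Two inconsistencies add to this: the principal investigator as home assessor against the blinded-assessor statement, and the order of written consent and baseline data in Section 3.3 against Section 3.2.

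The protocol does not show that any envelope can be read early, and no bias can be calculated from it. The false-positive rates of about 7% and 13% depend wholly on the assumed risks and on 4 or 8 of 40 infants per arm being steered. The fixed block size is a separate way of predicting allocations and is not counted here. The sample size is unaffected. This is an inexpensive improvement worth making before recruitment, because selection at enrolment cannot be reliably corrected afterwards.

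**What to change.** In Section 3.2, have the independent researcher who creates the list also keep it, and release each allocation by phone or message. Release only after the infant's identifier, Graf type, alpha angle, remaining baseline data and written consent have been logged.

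In Section 3.3, move the second explanation, written consent, ID number and questionnaire ahead of randomisation, so that both sections give one order.

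If envelopes are kept, the independent researcher, not the principal investigator, should prepare and hold them. They should be opaque, with cards of one colour, and each opening should be entered in a signed and timed log.

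Reconcile the blinded-assessor statement with the home ultrasounds. Taking the list away from the principal investigator removes one source of knowledge, but an assessor in the home may still see how the infant is dressed, so the text should say how these examinations are treated.

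The cost is a few sentences in two sections and about 80 short contacts over recruitment with someone already in the trial. The downside is that this researcher must be reachable before each discharge.

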3. STUDY METHODOLOGY

3.1. Study design

A prospective interventional randomized controlled trial with two study groups will be conducted in Mongolia.

“Swaddling” group: The newborns randomized into the “swaddling” group will be swaddled in the common traditional Mongolian method at least 20-24 hours every day for 4-6 weeks. Traditional swaddling in Mongolia is as follows: Swaddling is a tightly wrapping (2 adult fingers pass under the cloth) of a baby in several layers of cloth, covered by one warmer blanket from head and neck to toe in a straight position after birth for day and night time. Two or three ropes are used across a baby's body for binding to avoid unwrapping. Since the non-swaddling clothes have to be provided with alternatives to the readily available swaddling clothes and blankets, the swaddled group will be given a blanket and several cotton sheets at the time of recruitment.

“Non-swaddling” group: The “non-swaddling” group will be instructed not to swaddle at all for 4-6 weeks. The required size and warmth of clothing required to keep a newborn infant warmly clothed will be provided to the family. Also, wide warm sleeping bags that allow free legs movements will be provided to prevent swaddling when go outdoors.

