3.3. Data collection and quality control

After a routine standard physical examination on the first day of life, all newborns will be examined by hip ultrasound. The standardized and uniform system of Graf will be used for diagnostics.²² The hip ultrasound examination will be performed by a trained and experienced neonatologist using an ultrasound machines (GE Logiq series) with a linear array transducer operating on an ultrasound frequency of 7–10 MHz. A Sonofirst® holding cradle and transducer fixation unit (Orthopunkt, Solothurn) will be used to prevent tilting errors and to standardize examination techniques.^{14,22} A web-based, password-protected tool, “HipScreen” (WebWaren, Bern, Switzerland)¹⁴ will be used for quality control purpose. The tool enables the screener to upload DICOM files exported from the ultrasound machines. Four images (two per hip side; one of them with measured alpha and beta angles according to Graf), will be required. This will allow continuous and reliable review of hip grading, diagnosis of DDH, and treatment decisions. Trained, on-site experts will check all examinations and promptly send comments to the screener. Discrepancies between expert assessments will be resolved by discussion and consensus.

After identification of all term newborns with Graf Type 2a cases (physiologically immature) of the neonatologist/data collector will be listed and the newborns and their mothers will be undergoing the screening process by research assistants to see whether they meet the inclusion criteria. The parents of the physiologically immature cases will be given oral information about hip dysplasia and study purpose. Consequently, parents will give their oral consent to participate. Those who refuse consent will be registered, but will not be included.

After the randomization of eligible newborns with physiologically immature (Graf Type 2a) hips, the research assistants will explain and give detailed information about the study again to the parents in both “swaddled” and “non-swaddled” groups. The parents will be requested to sign an informed consent form if they agree to take part in the study before they are given an ID number. After the obtaining the written consent form, a brief questionnaire about demographic (e.g. birth date, gender of newborn etc.) and birth related information such as fetal position, birth weight, number of parity and family history of DDH will be filled by the research assistants.

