For babies assigned to the “swaddling” group, parents will be instructed to follow a pattern of traditional Mongolian swaddling as described above. For babies assigned to the “non-swaddling” group, parents will be instructed to do not swaddle at all and only use a wide sleeping bag with free leg position.

Trained research assistants will make home visits on weekly basis until the infants are 4-6 weeks of age to check and monitor the compliance of the families by observing the baby during every home visit and collecting retrospectively 24-hour diaries of swaddling and non-swaddling patterns. Also unscheduled visits from monitoring research assistants will be organized to estimate unreported non-compliance conducted for all families 2 to 3 times.

At 4-6 weeks follow up visit, the babies will be checked by Graf’s method of hip ultrasound performed by a trained radiologist uninformed about the initial status of the hips. Regardless of the study group, monthly controls will be fixed until complete maturation to Graf type 1 is documented. Families, who did not show up for follow-up will be contacted by phone or home

visit. In cases when the parents will not be able/willing to come to the follow-up control visit(s), the PI will visit the family and make the follow-up ultrasound examination at their home using a portable ultrasound device (MicroUs EXT-1H, REV:C). All infants in need of therapy (Graf type 2a-, 2c or worse) will be treated with Tubinger orthosis.

Monitoring: In the non-swaddling group, it is expected that some families would not adhere to their instructions of not swaddling because of grandparents/cultural pressures. To monitor compliance and obtain a measure of exposure, multiple sources of information will be used:

1. A retrospective 24-hour history of swaddling/clothing: will be recorded by research assistants during each weekly home visit through recording the carer's descriptions of the style of dress/clothing/ swaddling and length of each during the past 24-hour within the 24-hour retrospective diaries (a kind of behaviour diary adapted to record swaddling/clothing pattern)
2. Direct observation of research assistants during weekly visits: of the dressing/clothing/ swaddling of each child and discreetly recording observations of the type of baby clothing items that each family washed and hung to dry on the day of visit (available for observation during the majority of visits)

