3.4. Outcome assessments

The primary outcome of the study will be the number of “non-Type 1” hip cases at the any monthly follow-up ultrasound control visits.

The secondary outcomes are:

- a. number of DDH cases (Graf Type 2a-, Type C, D and Type 4) at any monthly follow-up ultrasound control visits
- b. correlation between the primary outcome and the swaddling frequency (in hours) per day and swaddling duration in days
- c. primary and secondary outcomes association with the swaddling.

Operational definitions

Swaddled: Newborns are swaddled in the common traditional Mongolian method at least 20 hours per day for 4-6 weeks

Non swaddled: Newborns are not swaddled at all.

The “non-Type 1” hip case: a neonate who’s Graf ultrasound type is other than Type 1 at any monthly follow-up visits

Physiologically immature or Graf Type 2a hip: has a certain degree of physiological delay in ossification of the bony acetabular roof. The alpha angle is between 50 and 59, the beta angle is between 55 and 77, and the patient is younger than 6 weeks of age.

Graf Types 2a- and 2a+: Starting from 55° alpha at 6 weeks of age and assuming a spontaneous maturation of 1° per week. Type 2a+ is still considered to be physiological while 2a- hips are assigned to the group of DDH.

Swaddling hours: according to the 24-hour diaries of swaddling and non-swaddling patterns of mothers and research assistants' compliance check reports

Swaddling days: according to the 24-hour diaries of swaddling and non-swaddling patterns of mothers and research assistants' compliance check reports

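### The protocol says the outcome radiologist is blinded, but the arms wear different study-supplied clothing up to the 4-6 week scan and no step conceals the arm.

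*Protocol*

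**What the plan says.** Section 3.2 of the protocol says that parents in the swaddling group and the research assistants will know the arm, but "the outcome assessor/radiologist will be kept blinded to the allocation".

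Section 3.1 fixes the exposure and the clothing. Infants in one arm are to be "swaddled in the common traditional Mongolian method at least 20-24 hours every day for 4-6 weeks", and "the swaddled group will be given a blanket and several cotton sheets at the time of recruitment". For the other arm, "wide warm sleeping bags that allow free legs movements will be provided to prevent swaddling when go outdoors". Section 3.3 repeats the instruction to those parents: do not swaddle, and "only use a wide sleeping bag with free leg position".

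Section 3.3 describes the first outcome visit at 4-6 weeks as "hip ultrasound performed by a trained radiologist uninformed about the initial status of the hips". What it withholds from the radiologist is the baseline hip status; it does not mention the arm. Section 3.4 defines a primary-outcome case as an infant whose "Graf ultrasound type is other than Type 1 at any monthly follow-up visits".

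Section 3.3 also describes a quality-control step in which "Trained, on-site experts will check all examinations and promptly send comments to the screener". It does not say whether those experts are masked, or whether their reading counts as the outcome.

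**The concern.** The protocol makes a specific claim of assessor blinding, but its own procedures work against that claim and nothing it describes supports it. The two arms differ in something that can be seen on the infant, and the person who reads the outcome meets the infant face to face at the end of the assigned period. That person also meets a parent who knows the allocation and has not been asked to keep it back.

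This matters because the primary outcome depends on a measured angle. The background section uses 60 degrees of alpha as the threshold, and section 3.4 places Type 2a at 50 to 59 degrees. Infants enter the trial with Type 2a hips, so some follow-up readings can be expected close to the cut. Section 6 states the team's expectation that swaddling harms these hips. A reader who recognises the arm and shares that expectation could move borderline hips across the cut in the hypothesised direction. The trial would then report part of that shift as a swaddling effect, under a statement that the assessor was blinded.

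**Working it through.** **1. The passages side by side (section 3 throughout)**

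| Question | What the protocol gives |
|---|---|
| Is the assessor said to be blinded? | Yes (3.2) |
| Does the arm change what the infant is dressed in? | Yes, with study-supplied items in both arms (3.1, 3.3) |
| Until when? | 4-6 weeks (3.1) |
| When is the first outcome scan? | 4-6 weeks (3.3) |
| Does the assessor see the infant? | Yes, the radiologist performs the scan (3.3) |
| What is withheld from the assessor at that visit? | Baseline hip status (3.3) |
| Who undresses the infant, and where? | Not stated |
| Are parents asked not to disclose? | Not stated |
| Is there a masked reading that defines the outcome? | Not stated |

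The protocol itself treats dress as evidence of exposure: research assistants record each child's clothing, and the items hung out to dry, to judge compliance (3.3).

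**2. Why the first scan carries most of the weight**

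An infant counts as a case if any monthly visit shows a hip other than Type 1 (3.4). Monthly controls continue until Type 1 is documented (3.3). So an infant read as non-Type 1 at the first scan is already a case, and an infant read as Type 1 has finished the monthly controls. For infants who attend, the first scan essentially settles the primary outcome. It is also the scan closest to the assigned clothing.

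**3. The design effect, for scale**

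Section 3.2 assumes 10% against 40% non-Type 1. The worked line reproduces: 7.9 × (0.1×0.9 + 0.4×0.6) / 0.3² = 7.9 × 0.33 / 0.09 = 28.97, rounded up to 29 per group. The plan is to enrol about 40 per group. The blinding point does not change this figure; it supplies the 30-point effect and the 10% rate used below.

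**4. Illustration of reader bias**

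Assumptions, none of them from the documents except the 10% rate and the 60-degree cut: follow-up alpha is normal with SD s of 3, 4 or 5 degrees; one angle decides each infant's status; and a reader shifts the reading by d degrees.

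- Mean: m = 60 + 1.2816 × s, so that P(alpha < 60) = 0.10.
- Rate after a shift d: Φ((60 − m − d) / s) = Φ(−1.2816 − d/s).

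| SD | Mean | d = −1 | d = −2 | d = +1 | Gap, −1 against +1 |
|---|---|---|---|---|---|
| 3 | 63.8 | 17.2% | 26.9% | 5.3% | 11.8 points |
| 4 | 65.1 | 15.1% | 21.7% | 6.3% | 8.8 points |
| 5 | 66.4 | 14.0% | 18.9% | 6.9% | 7.1 points |

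Gaps are taken before rounding.

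With no true effect and 40 per group, the exact rejection rate of the two-sided 5% chi-square test (summing both binomials over all tables) is 0.06 without bias. It becomes:

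- 0.09-0.16 if swaddled hips are read 1 degree low;
- 0.21-0.51 if they are read 2 degrees low;
- 0.19-0.42 if swaddled hips are read 1 degree low and non-swaddled hips 1 degree high.

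**5. A second illustration without angles**

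Suppose the true rate is 10% in both arms and a fraction b of truly Type 1 swaddled infants is called non-Type 1. The observed swaddled rate is 0.10 + 0.90b: 14.5%, 19% and 28% for b = 5%, 10% and 20%. With 40 per group the false-positive rate is then 0.10, 0.21 and 0.56. At a common true rate of 40% the same fractions give 0.06, 0.09 and 0.20, so the result depends strongly on the underlying rate.

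**The case against.** A reader might infer that the arm is visible at every clinic scan and that blinding is therefore broken. The documents do not support this, for four reasons.

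- **Arrival clothing is not stated.** The outdoor sleeping bag and the near-continuous swaddling make it a reasonable inference. But an infant has to be unwrapped for a hip scan, and the protocol does not say where or by whom. Nor does it say that parents talk about care at home.
- **Clothing is an imperfect clue.** The protocol calls swaddling common and the cloths readily available, and it expects some non-swaddling families to swaddle. A wrapped infant is not proof of the swaddling arm. The sleeping bag is the more distinctive item.
- **The instructions end at 4-6 weeks.** Later monthly visits fall after that period, and the clue is weaker there. This limits the reach of the point but does not remove it, because the first scan largely decides the outcome.
- **The size is not established.** The SD, the single-angle model and the reader shift are all assumed. The outcome is per infant, with both hips imaged. The stated hypothesis is the team's, and nothing says that the radiologist shares it.

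It might also seem natural to make the experts' consensus the primary outcome. The text gives poor support for that. Their check is described as quality control with comments sent to the screener, a word that section 3.2 uses for the neonatologists. Section 3.5 uploads all pictures to the platform, but upload is not grading. The stored frames are chosen by the person scanning, and one per hip carries measured angles. A later consensus could also differ from the reading that ended follow-up or led to treatment.

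These limits stand. What remains is a stated blinding with no procedure behind it, at the visit where the arms look most different.

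**Conclusion.** The concern holds in a limited form. Followed as written, the protocol makes it likely, though not certain, that the arm is apparent to the radiologist at the 4-6 week scan, and that scan largely settles the primary outcome. Because the protocol claims blinding while its own procedures undermine it, this is more than a missing detail, and it should be corrected.

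The size of any bias is unknown. Under the assumptions above, a consistent 1-degree tendency would produce a false difference of about 4-7 points if it affects the swaddled arm only (14.0-17.2% against 10%), or about 7-12 points if it runs in opposite directions in the two arms. The design effect is 30 points. A reading tendency of that size would not by itself produce the planned effect, but it could add to a real one or raise the false-positive rate. These figures show why masking is worth securing; they do not estimate what will happen.

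**What to change.** In section 3.3, for each follow-up scan at the clinic:

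1. Before the radiologist enters, existing staff undress the infant, cover it with one neutral sheet and put all study clothing out of sight. The radiologist still does the positioning and scanning, so that no one who knows the arm influences the image.
2. Parents are asked beforehand not to mention how the infant is cared for at home.
3. The radiologist's reading stays the primary outcome. A sensitivity analysis uses the experts' reading of the unmeasured HipScreen image of each hip, labelled by code only, with no arm, name or baseline scan. Section 3.3 asks for two images per hip, one with measured angles, so on that reading an unmeasured image should exist for each hip. The text should say explicitly that this expert reading covers follow-up scans.
4. State that the masked reading cannot remove bias in how the images were acquired. This is why steps 1 and 2 are needed as well.

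The cost is a few minutes per visit and coded image labels. If the experts' existing check does not already cover follow-up scans, the added reading at the first outcome visit is at most about 2 × 40 infants × 2 hips = 160 images. The sample size and the primary analysis do not change.
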